After the experimental and control groups agreed to participate in this study and completed the consent forms, the two groups took pre-tests, which measured the Chinese version of the CAT, the CSSAQ, and the PEFR, within 48 hours of hospitalization, which served as the baseline of the intervention (T0). Data were collected again on the 7th day (T1) and the 30th day (T2) of the intervention to evaluate the effect of the intervention on pulmonary function. Only the experimental group received bubble PEP training, while the control group had routine medical care. If participants were discharged from the hospital in the middle of the study, the investigator monitored the intervention effectiveness via weekly follow-up telephone calls.

The study procedures are shown in Figure 1. Of the 57 patients who met the criteria were invited to participate for study eligibility. 14 of the remaining 27 participants, 13 and 14 were assigned to the intervention and control groups, respectively. 7days follow-up (T1) data were obtained for 17 of the participants. 1M follow-up (T2) analyses were performed among the 14 participants with complete data. The attrition rates were 30% and 71% for the experimental and control groups, respectively, with an overall attrition rate of 52%.

Ethical considerations

The study protocol was reviewed and approved by the Institutional Review Boards of Fu Jen Catholic University Hospital and En Chu Kong Hospital (FJUH109078 & ECKIRB1091006). Participants were required to sign informed consent forms before

the study and were allowed to terminate or withdraw from the study at any time. Data collected from the participants were coded, de-identified, and kept in a locked cabinet (ClinicalTrials.gov number: NCT04828837).

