**Title: Bubble PEP Training Among Patient
With Chronic Obstructive Pulmonary
Disease in Pulmonary Function Effects**

Statistical Analysis

Principal Investigator : [name]
ClinicalTrials.gov number: NCT04828837

2021/02/25

Statistical Analysis

Statistical analyses were performed using the IBM statistical software SPSS Statistics version 22. The intention-to-treat analysis (ITT) method was employed for data analysis, and the expectation-maximization algorithm (EM) was used to handle missing data. We used t-tests for independent samples, and Fisher's exact tests when more than 20% of cells have expected frequencies <5 or less than 10 observations to examine the homogeneity between groups based on demographic characteristics. Descriptive statistics, including count, percentage, mean, and standard deviation, were used to summarize the data. The intervention effect was evaluated using the generalized estimating equation (GEE) statistical method. Two-tailed tests were conducted, and p-values less than .05 were considered statistically significant.

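### The Protocol's 14 completers at day 30 conflict with its own attrition rates, which give 13, and it is unclear whether T2 was analysed on completers or on all 27

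*Protocol*

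**What the plan says.** Protocol, Procedures, in order:

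- Arm sizes: "14 of the remaining 27 participants, 13 and 14 were assigned to the intervention and control groups, respectively". The start of the sentence is garbled, but 13 + 14 does equal 27.
- Day 7: "7days follow-up (T1) data were obtained for 17 of the participants".
- Day 30: "1M follow-up (T2) analyses were performed among the 14 participants with complete data".
- Loss: "The attrition rates were 30% and 71% for the experimental and control groups, respectively, with an overall attrition rate of 52" per cent.

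SAP, Statistical Analysis: "The intention-to-treat analysis (ITT) method was employed for data analysis, and the expectation-maximization algorithm (EM) was used to handle missing data". On the effect estimate: "The intervention effect was evaluated using the generalized estimating equation (GEE) statistical method". The SAP mentions no completers analysis. It does not list the variables in the EM model, and it does not say whether the GEE standard errors allow for values having been filled in.

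The Protocol cites Figure 1 for participant flow. The figure is not visible in the text available to me and may hold the counts by arm.

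**The concern.** There are three linked problems, with different degrees of certainty.

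1. **Count (high confidence).** The number with complete day-30 data and the three attrition rates cannot all be right for arms of 13 and 14.
2. **Analysis set (moderate confidence).** Read literally, the day-30 sentence describes an analysis of completers only, which is not what the SAP specifies.
3. **Handling of filled values (undocumented).** If the SAP was followed, about half the T2 values were filled by EM, and nothing says how the GEE treated them.

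A reader therefore cannot tell whether the T2 result rests on 13 completers, on 14, or on all 27 with about half the values filled. By the rates, only 4 control participants were observed at T2. In an arm that small, one participant more or fewer matters, and the method for the missing values largely determines the result.

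**Working it through.** **Step 1: counts.** Inputs from the Protocol, Procedures: 13 and 14 assigned, 14 complete at T2, attrition 30%, 71% and 52%. Attrition = lost / assigned. I compared every whole-number pair of losses with the two arm rates.

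| Arms (bubble PEP, control) | Lost | Arm rates | Overall | Complete | Largest miss on an arm rate |
|---|---|---|---|---|---|
| 13, 14 | 4, 10 | 30.8%, 71.4% | 14/27 = 51.9% | 13 (9 + 4) | 0.8 points |
| 13, 14 | 4, 9 | 30.8%, 64.3% | 13/27 = 48.1% | 14 (9 + 5) | 6.7 points |
| 13, 14 | 3, 10 | 23.1%, 71.4% | 13/27 = 48.1% | 14 (10 + 4) | 6.9 points |
| 14, 13 (swapped) | 4, 9 | 28.6%, 69.2% | 13/27 = 48.1% | 14 (10 + 4) | 1.8 points |

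- For the arm sizes as stated, (4, 10) is the only pair that fits both arm rates at any tolerance from 0.8 to 6.7 points. It also gives the stated 52%.
- 4/13 would normally be written 31%, but no other count is close to 30% (3/13 = 23.1%).
- Swapping the arms brings the arm rates near but misses the overall rate by 52 − 48.1 = 3.9 points.
- The 52% is not a day-7 figure: (27 − 17)/27 = 37.0%.
- With 14 complete, 52% would need 29 assigned: (29 − 14)/29 = 51.7%. The text says 27.
- The stated 14 equals the number lost according to the rates, so a drafting slip is plausible.

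**Step 2: if T2 used completers only.** Standard error of a difference in means, in SD units (t-test approximation):

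- 9 against 4: √(1/9 + 1/4) = 0.60
- 13 against 14: √(1/13 + 1/14) = 0.39

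**Step 3: if T2 used all 27 with EM.** I simulated the GEE arm-by-time contrast at T2.

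- From the Protocol: arms of 13 and 14, T2 losses of 4 and 10, and 10 losses in total at T1.
- Assumed, because the documents do not give them: normal outcomes, complete T0 data, exchangeable correlation of 0.3, 0.5 or 0.7, T1 losses split 3 + 7 or 0 + 10, completely random loss, and a conditional-mean EM fill.
- Test: robust standard error, |z| > 1.96. There were 1,000 runs per setting for the arm-in-EM results.

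| Handling of missing values | False positives at nominal 5% | Other result |
|---|---|---|
| All 27 observed (reference) | 7% to 8% | – |
| EM with arm, filled values treated as observed | 31% to 37% | reported SE is 47% to 55% of the true one |
| Same, 14 completers (4 + 9 lost), 600 runs | 28% | correlation 0.5, T1 losses 3 + 7 |
| Same, 14 completers (3 + 10 lost), 600 runs | 32% | correlation 0.5, T1 losses 3 + 7 |
| EM without arm | 5% to 7% | true 1.0 SD effect estimated at 0.41 to 0.55 SD (300 runs) |
| GEE on observed data, ordinary robust SE, 300 runs | 10% to 11% | T1 losses 3 + 7 |
| GEE on observed data, small-sample corrected SE, 300 runs | 5% to 6% | T1 losses 3 + 7 |

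Example of the SE ratio at correlation 0.3: 0.355/0.657 = 54%. Simulation error (1 SE) is about 1.5 points for the 1,000-run rates near 0.3 and 1 to 2 points for the 300-run rates.

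**The case against.** - **Attrition is not defined.** If it meant withdrawal from the study or the training, one person counted as lost could still have T2 data, and both figures could stand. The documents do not exclude this, but they give no such definition, and the rates directly follow the T2 count. If it is the explanation, it needs to be stated.
- **The arm sizes are a weak anchor.** The sentence giving them is garbled, Figure 1 is not visible, and the swapped arms come within 1.8 points of both arm rates with 14 completers. It is right not to declare which figure is wrong. Even so, the swap does not rescue the 52%.
- **It is one participant.** Taken alone, this is a correction to a flow count. However, these are exact head counts, and by the rates the control arm has only 4 completers.
- **The T2 sentence may only describe flow.** It stands between the day-7 count and the attrition rates, and the SAP states intention to treat without qualification. This stands, and is why the analysis-set point carries moderate confidence only.
- **The high false-positive rate depends on unstated choices.** It needs arm in the EM model, a single fill, and filled values treated as observed; nothing shows that this was done. But leaving arm out exchanges the false positives for an effect shrunk by about half, so the SAP's silence matters either way.
- **The correlation range stops at 0.7.** The Protocol reports an ICC of 0.8 for the CAT, of unspecified type. A further check at 0.8 gave about 40% false positives, so 31% to 37% is not an upper bound.

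**Conclusion.** The concern holds. The day-30 count and the attrition rates disagree by one participant: 13 complete (51.9% lost) by the rates, or 14 complete (48.1% lost) as written. This is arithmetic on stated figures. It assumes only that attrition means having no T2 data and that the arm sizes are as printed. Which figure is wrong cannot be settled from the documents.

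Whether T2 was analysed on completers or on all 27 is unresolved, and either answer has a material consequence. The completers reading raises the standard error from 0.39 to 0.60 SD and drops the comparison as randomised, with very unequal loss between arms. The SAP's reading can mislead even under completely random loss, through standard errors about half their true size or through an effect shrunk by about half, depending on EM details that are not given. Those sizes rest on the simulation assumptions listed above; missingness by outcome is not reported. This should be fixed before the T2 p-value is relied on.

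**What to change.** 1. **Counts.** Check the flow against source records and Figure 1, and correct the T2 number, the rates, or both. If the rates are right, the text should give 13 completers (9/13 and 4/14) and attrition of 31%, 71% and 52%. Define attrition, and report the number observed in each arm at T1 and T2.
2. **Analysis set.** Establish from the analysis file which participants entered the T2 model, and state it identically in both documents. If all 27 were analysed, reword the Protocol sentence as participant flow. If completers were used, make the SAP's analysis of all 27 as assigned the main result and label the completers result a sensitivity analysis.
3. **Missing values.** List the variables in the EM model, including whether arm was one, and say how the GEE standard errors treat filled values. If these were treated as observed, do not rely on that p-value; re-estimate with a method that carries the uncertainty of filling, for example multiple imputation of the same 27 with arm in the model, followed by GEE. I have not tested multiple imputation at this sample size, and with perhaps 4 observed control values its result will be imprecise. In either case report the GEE on observed data alongside, with a small-sample corrected standard error.
4. **Labelling.** Mark anything added after the data were seen as post hoc.

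The cost is a check of the flow counts and the analysis output, wording in both documents, and one GEE run on observed data. Re-estimation of T2 is needed only if completers were the main set or filled values were treated as observed. No new data are needed.

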**Title: Bubble PEP Training Among Patient
With Chronic Obstructive Pulmonary
Disease in Pulmonary Function Effects**

Statistical Analysis

Principal Investigator : [name]
ClinicalTrials.gov number: NCT04828837

2021/02/25

Statistical Analysis

Statistical analyses were performed using the IBM statistical software SPSS Statistics version 22. The intention-to-treat analysis (ITT) method was employed for data analysis, and the expectation-maximization algorithm (EM) was used to handle missing data. We used t-tests for independent samples, and Fisher's exact tests when more than 20% of cells have expected frequencies <5 or less than 10 observations to examine the homogeneity between groups based on demographic characteristics. Descriptive statistics, including count, percentage, mean, and standard deviation, were used to summarize the data. The intervention effect was evaluated using the generalized estimating equation (GEE) statistical method. Two-tailed tests were conducted, and p-values less than .05 were considered statistically significant.

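### One EM-filled dataset analysed by GEE as if observed would make the T2 test far too liberal or roughly halve the effect, and the Protocol describes a different T2 analysis

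*SAP*

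**What the plan says.** The SAP (Statistical Analysis) gives the analysis in a few sentences. "The intention-to-treat analysis (ITT) method was employed for data analysis", and "the expectation-maximization algorithm (EM) was used to handle missing data". For the effect, "The intervention effect was evaluated using the generalized estimating equation (GEE) statistical method". The criterion is: "Two-tailed tests were conducted, and p-values less than .05 were considered statistically significant". It does not say how the EM result was carried into GEE, whether treatment group was in the EM model, which contrast was tested or which standard error was used.

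The Protocol (Procedures) reports 13 patients assigned to training and 14 to control. It then says "7days follow-up (T1) data were obtained for 17 of the participants" and "1M follow-up (T2) analyses were performed among the 14 participants with complete data". The next sentence reads "The attrition rates were 30% and 71% for the experimental and control groups, respectively, with an overall attrition rate of 52" per cent.

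**The concern.** EM estimates the parameters of a distribution, whereas GEE needs a dataset. Since the SAP mentions neither multiple imputation nor a variance correction, the natural reading is that each missing value was replaced once by its conditional mean and the filled data were analysed as if observed. That is an inference; the SAP does not say it. It would harm the T2 result in one of two ways.

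- **Group in the EM model.** Filled values have no residual scatter but count as measurements, so standard errors carry no penalty for the missing data.
- **Group not in the EM model.** Missing controls are filled partly from the experimental arm, and the group difference shrinks.

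Separately, intention-to-treat on 27 patients with EM and an analysis of 14 completers cannot both describe T2. T2 is the end of the 30-day training and the visit with the heaviest loss, and a reader cannot tell which analysis its p-values come from.

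**Working it through.** **1. Attrition, from the Protocol's figures.** 4/13 = 30.8%, 10/14 = 71.4% and 14/27 = 51.9% reproduce the stated 30%, 71% and 52%. They leave (13 − 4) + (14 − 10) = 9 + 4 = 13 completers. Fourteen completers would mean 13/27 = 48.1% lost.

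**2. Hand check of both mechanisms.** Take the limiting case of no correlation between visits, with 9 v 4 observed at T2 and outcome SD 1.

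- *Group in EM.* Each missing value becomes its arm mean and adds nothing to the sum of squares. The reported robust variance is about 8/13² + 3/14² = 0.0473 + 0.0153 = 0.0626 (SE 0.25). The true variance is 1/9 + 1/4 = 0.361 (SD 0.60). The ratio is 0.25/0.60 = 0.42, so the 1.96 cut-off acts like 1.96 × 0.416 = 0.82, which a standard normal exceeds in absolute value about 41% of the time.
- *Group not in EM.* With true effect δ, every missing value becomes the pooled completer mean, (9/13)δ = 0.692δ. The arm means are (9 + 4 × 0.692)/13 = 0.905δ and (10 × 0.692)/14 = 0.495δ. The difference is 0.41δ.

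**3. Simulation with correlated visits.** Assumptions not in the documents: normal data; between-visit correlation 0.3, 0.5, 0.7 or 0.8; monotone dropout, missing completely at random; T1 observed in 11 v 6 (only the total of 17 is stated). The test is group-by-T2 (T2 minus T0) in a saturated group-by-time GEE with uncorrected robust SE. There were 4,000 trials per setting; the Monte Carlo SE at 34% is √(0.34 × 0.66/4000), about 0.7 points.

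| Type I error at nominal 5%, 9 v 4 completers | 0.3 | 0.5 | 0.7 | 0.8 |
|---|---|---|---|---|
| EM fill, group in model | 29% | 34% | 36% | 37% |
| EM fill, group omitted | 6% | 7% | 6% | 6% |
| GEE on observed values | 10% | 11% | 10% | 9% |
| GEE, completers only | 12% | 13% | 12% | 12% |

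Full data on 13 v 14 give about 7%. The EM fill with group therefore adds between 29 − 12 = 17 and 37 − 9 = 28 percentage points to what the small sample and uncorrected SE already cause. At correlation 0.5 the average reported SE is 0.29 against a true SD of 0.58.

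With group omitted, a true 1 SD effect at T2 behaves as follows:

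- No effect at T1: estimated as 0.41 SD; 95% interval coverage 60%/50%/32%/20% across the four correlations.
- Full effect already at T1: estimated as 0.48–0.52 SD; coverage 65%/57%/46%/37%.

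**4. Sensitivity.**

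- T1 split 10/7 or 12/5: 34% at correlation 0.5.
- Fourteen completers, at 0.3/0.5/0.7: 28%/32%/34% (10 v 4) or 26%/30%/32% (9 v 5).
- A separately programmed simulation, which also tried AR(1) correlation, gave 27–38% with group and 0.36–0.55 of the effect without.
- In that simulation an ordinary t-test on the filled data (group in EM) still rejected 25–35%, while a t-test on available cases rejected 4–5%. Most of the excess therefore comes from the filling, not from GEE.

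**5. Candidate remedies under the null** (9 v 4, correlation 0.3/0.5/0.7).

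| Analysis | Type I error |
|---|---|
| REML repeated measures, Satterthwaite | 6.2% / 6.5% / 4.8% |
| REML repeated measures, Kenward-Roger | 5.8% / 5.9% / 4.1% |
| GEE on observed values, Mancl-DeRouen SE | 5.3% / 5.9% / 5.2% |
| Completers only, Mancl-DeRouen SE | 7.0% / 7.1% / 6.7% |
| Multiple imputation with group, small-sample df | 2.1% / 2.7% / 2.5% |
| EM-filled data, Mancl-DeRouen SE | 26% / 30% / 32% |

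The REML and multiple-imputation rows use 1,500 trials; median REML df is 10–11. Correcting the SE after the EM fill does not cure the problem.

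**The case against.** The SAP never says that a single filled dataset was analysed, and the only explicit statement of the T2 analysis set, in the Protocol, points to completers. If that is what was done, the EM problem disappears at T2 and the error is about 12–13%, part of which (about 7%) is present even with full data. This stands: the 26–37% belongs to one reading, and the certain defect is the contradiction. But the contradiction cannot be settled from the documents, and neither EM reading gives a sound T2 result.

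The contrast is also unstated. For the group difference at T2 alone, the rejection rate with group in EM ranged from about 17% to 39% across runs, falling as the correlation rises. The quoted range is therefore specific to the group-by-T2 test, though even the lowest figure is over three times nominal.

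The 13-or-14 discrepancy may be a simple slip, since 14 is also the number lost. It needs correcting but adds nothing to the EM argument.

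Finally, a REML model with unstructured covariance is ambitious with about 4 controls at T2. Its convergence and power were not examined, nor was whether the named SPSS version offers these corrections. That is a reason to accept simpler valid options, not to keep the EM fill.

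**Conclusion.** The concern holds; the plan is wrong as written. Two things follow from the documents alone: the SAP and the Protocol describe different T2 analyses, and the stated attrition implies 13 completers against the stated 14.

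The size of the harm depends on which analysis was run. A single EM fill with group gives about five to seven times the nominal error (26–37%) for the group-by-T2 test. Without group, a real effect is understated by about half and its interval is usually misplaced. Completers only with an uncorrected robust SE is moderately anti-conservative. Confidence in the exact figures is medium, because correlation, T1 losses by arm and the dropout mechanism are assumed. Missing completely at random is a favourable assumption here; losses as unequal as 71% and 30% make informative dropout plausible.

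**What to change.** 1. **Reconcile the documents.** State the T2 analysis set, the number of completers by arm, how EM was applied and whether group was in it.
2. **Do not analyse one EM-completed dataset as observed.** Analyse the observed T1 and T2 values with small-sample inference. Preferred: a REML repeated-measures model with group, time, group × time, T0 and T0 × time, unstructured covariance, and Satterthwaite or Kenward-Roger df. Equally acceptable for this defect: GEE on the observed values with a Mancl-DeRouen SE. If imputation is kept, use proper multiple imputation with group in the model and Rubin's rules with small-sample df, accepting that it was conservative in simulation.
3. **State the limit of the evidence.** If dropout was monotone, the 27 − 17 = 10 patients with no T1 value add little or nothing to the T2 estimate, so the result should not be presented as full intention-to-treat evidence.
4. **Add a shift sensitivity analysis** and a caution that missing-at-random may fail. If dropouts in both arms differ from observed patients by 1 SD at T2, the group difference moves by 10/14 − 4/13 = 0.41 SD. If only control dropouts differ, it moves by 10/14 = 0.71 SD.

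The cost is revised wording and a re-analysis, possibly in other software; no new data are needed. Intervals will be wider: at correlation 0.5 the true SD of the T2 estimate is about 0.55–0.6 SD, against a reported 0.29 after an EM fill with group. Some significant results may disappear.

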**Title: Bubble PEP Training Among Patient
With Chronic Obstructive Pulmonary
Disease in Pulmonary Function Effects**

Study Protocol

Principal Investigator : [name]
ClinicalTrials.gov number: NCT04828837

2021/02/25

Material and Methods

Design and Participants

A randomized controlled trial with a single-blind study design was conducted. Using convenience sampling, data were collected from February 2021 to July 2021 at two teaching hospitals in northern Taiwan. Random serial numbers were generated by a research assistant using Random Allocation Software. The research assistant then put each serial number into an opaque envelope. After agreeing to participate in this study, each participant received an envelope and opened it to find out whether they belonged to the experimental group or the control group. The research assistant who assisted with recruitment did not engage in data collection or analysis.

The inclusion criteria were patients who diagnosed AECOPD and were 40 years old or older, conscious, could read articles, agreed to participate in the study, and signed an informed consent document. Exclusion criteria included patients who had used non-invasive PEP treatment before or during hospitalization, who had a mental disorder. The G*Power 3.1.9.7. software was used to estimate the sample size. A sample size of at least 26 has 80% power to detect the largest effect size of 0.5. An alpha level of 0.05 was used.

Measurements

The participants' demographics and clinical characteristics were collected, including gender, age, marital status, occupation, smoking history, chronic comorbidities (hypertension, diabetes mellitus, heart disease, lung cancer, and pneumothorax), COPD stage and dry powder bronchodilator use.

Chinese Version of the CAT

A total of eight items were used to assess the degree of dyspnea of the patients. Each item had a score ranging from 0 to 5 points, with the highest total score being 40

points. The higher the score, the higher the degree of dyspnea (Pothirat et al., 2015). The present study Cronbach's α was 0.88, and the Intraclass Correlation Coefficient (ICC) was 0.8.

CSSAQ

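### Significance tests on demographics cannot show that 13 and 14 patients are balanced, and they say nothing about the roughly half who supply T2 after 30% versus 71% attrition

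*SAP*

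**What the plan says.** The SAP's Statistical Analysis section gives the method: "We used t-tests for independent samples, and Fisher's exact tests when more than 20% of cells have expected frequencies <5 or less than 10 observations". The stated purpose is "to examine the homogeneity between groups based on demographic characteristics". The threshold applies throughout: "Two-tailed tests were conducted, and p-values less than .05 were considered statistically significant". Descriptive statistics are planned, the effect is evaluated by GEE with no model terms named, and under ITT "the expectation-maximization algorithm (EM) was used to handle missing data".

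The protocol's Measurements section collects more than demographics, including comorbidities and "COPD stage and dry powder bronchodilator use". Its Procedures section has CAT, CSSAQ and PEFR measured at T0. The SAP's homogeneity sentence names neither the clinical characteristics nor the T0 outcomes.

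On patient numbers, Procedures says "14 of the remaining 27 participants, 13 and 14 were assigned to the intervention and control groups, respectively", then "The attrition rates were 30% and 71% for the experimental and control groups, respectively, with an overall attrition rate of 52" per cent. It adds that "1M follow-up (T2) analyses were performed among the 14 participants with complete data". Neither document plans a comparison of baseline characteristics for the patients who supply T2, either by arm or against those lost.

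**The concern.** A baseline significance test in a randomised trial tests a hypothesis already known to be true. A small p-value is chance, and a large one is not evidence of balance, least of all with 27 patients. The only stated use of these tests is to examine homogeneity, so a table of non-significant results invites the reader to conclude that like is being compared with like.

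The larger gap is at T2. Randomisation covers all 27 patients. It does not cover those still observed at 30 days, when one arm has lost less than a third of its patients and the other more than two thirds. If loss is related to disease severity, the retained groups can differ prognostically even though the randomised groups did not. A table of the 27 cannot reveal this, and the plan names no covariate that would adjust for it.

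**Working it through.** **Inputs.** 13 and 14 assigned, attrition of 30%, 71% and 52%, and 14 with complete T2 data (Protocol, Procedures); two-sided alpha 0.05, t-test and Fisher's exact test (SAP).

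**1. The plan's own attrition figures.**
- Experimental: 4/13 = 30.8%. Control: 10/14 = 71.4%. Overall: (4 + 10)/27 = 14/27 = 51.9%. These fit the stated rates to within rounding or truncation.
- They leave 9 + 4 = 13 completers. The 14 completers stated would mean 13/27 = 48.1% overall attrition.
- The figures conflict by one patient. On either count about half remain (13/27 = 48.1% or 14/27 = 51.9%).

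**2. What the t-test can detect among 27 patients.**
- Smallest significant standardised difference = t(0.975, 25 df) × √(1/13 + 1/14) = 2.060 × 0.385 = 0.793 SD.
- As a gauge of sensitivity, noncentral-t power against a 0.5 SD difference is 24%.
- By chance alone (normal approximation), randomisation at this size gives an imbalance above 0.5 SD with probability 2 × [1 − Φ(0.5/0.385)] = 19%.

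**3. What Fisher's exact test can detect.**
- Across all 2×2 tables with margins 13 and 14, the largest non-significant gap is 3/13 (23.1%) versus 9/14 (64.3%): 41.2 points, p = 0.054.
- This is a maximum, not a uniform threshold: 4/13 versus 0/14 (30.8 points) gives p = 0.041.
- It depends on how the SAP's trigger is read. In the 3/13 versus 9/14 table the smallest expected count is 12 × 13/27 = 5.8, so the expected-frequency condition is not met. The condition on fewer than 10 observations is met if read per cell, because four cells summing to 27 cannot all reach 10.
- If only the expected-frequency condition counted and uncorrected Pearson chi-square were used otherwise (the SAP does not name it), this table would give p = 0.031. The largest gap passed would then be about 35 points (12/13 versus 8/14, Fisher p = 0.077).

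**4. The same tests among completers.**
- With 9 and 4: t(0.975, 11 df) × √(1/9 + 1/4) = 2.201 × 0.601 = 1.32 SD. Fisher can pass 6/9 versus 0/4 (67 points, p = 0.070).
- With 14 completers the t-test limit is 1.29 SD for a 10/4 split and 1.22 SD for 9/5.
- Repeating the tests at T2 is therefore no remedy.

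**5. The attrition itself as an example.** Retention of 9/13 versus 4/14, a gap of 69.2% − 28.6% = 40.7 points, gives Fisher p = 0.057. The trigger caveat in step 3 applies here too, since all expected counts are at least 13 × 13/27 = 6.3. If there were 14 completers, p would be 0.021 (10/4) or 0.128 (9/5).

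**The case against.** The strongest reply is that the tests do no inferential work. The SAP states no pass/fail rule, and nothing in the GEE, its covariates or its population depends on them. Deleting them alone changes no estimate, interval or p-value. This stands, and it limits the harm to what readers are led to believe and to what the plan leaves out.

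Second, means, SDs and counts are planned, so standardised differences for the 27 could be derived from the report. That is largely true for the variables reported, but it does not help with retained and lost patients, for whom no table is planned.

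Third, T2 is a missing-data question, and ITT with EM would use all 27. In part this stands. But the SAP does not say which variables enter EM, and EM can only correct for loss explained by variables it is given. The protocol also describes the T2 analysis as one of patients with complete data, which does not sit easily with EM on 27.

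Fourth, the remedy is itself imprecise: at 9 versus 4 a standardised difference has a standard error of about √(1/9 + 1/4) = 0.60. This stands. The tables should describe and not decide, and covariates should not be chosen by whether they appear to predict loss in 27 patients.

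Finally, a stage main effect does nothing for a group-by-time contrast when data are complete and balanced; the contrast is then exactly unchanged. It matters when T2 loss depends on stage, which is the situation of concern here.

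**Conclusion.** The point holds as a low-cost improvement, not as a flaw that invalidates the analysis. With 13 and 14 patients the planned tests cannot show balance: the limit is 0.79 SD for the t-test and at most 41 points for Fisher where it applies (about 35 if Pearson chi-square replaces it under the narrower trigger). They leave unexamined the roughly half of patients who supply T2. Whether the retained groups actually differ is unknown.

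A reader might infer three stronger things that the documents do not support.
- *That a missed imbalance moves the effect by a known amount.* Multiplying 0.793 SD by an assumed correlation of 0.3 to 0.5 gives 0.24 to 0.40 SD, but only for an unadjusted comparison at a single visit. The GEE terms are not stated. If the effect is a change-from-T0 contrast and the covariate relates equally to both visits, the shift is 0. The range therefore starts at 0.
- *That a spurious flag is likely.* Twelve independent tests at 5% give 1 − 0.95^12 = 46%, but the SAP names only demographic characteristics, perhaps four or five of the twelve variables listed. For four at 5% each the figure is 1 − 0.95^4 = 19%. Fisher's actual error rate is below 5% and close to zero for rare characteristics. No single figure can be given.
- *That the tests would declare COPD stage balanced.* Read literally, the SAP does not test COPD stage at all.

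**What to change.** 1. Replace the baseline p-values with descriptive standardised differences by arm, for all randomised patients and separately for those retained and those lost at T2. Include COPD stage and T0 CAT, CSSAQ and PEFR. State that homogeneity will not be inferred from non-significance.
2. Pre-specify COPD stage (two levels, cut-point fixed in advance, since the documents give none) and the T0 value of the outcome as GEE covariates. T0 then serves as a covariate and not also as a response, so the SAP should say that T1 and T2 are the modelled visits.
3. Include arm, COPD stage and the T0 outcomes in the missing-data model. Do this whatever the tables show, and do not select variables by their apparent association with loss.
4. Reconcile the 14 completers with the 13 implied by the arm rates, and state whether the T2 analysis uses completers or all 27.

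The cost is about one degree of freedom for COPD stage, extra descriptive tables and a few sentences in the SAP. Items 2 and 3 change the effect and missing-data models, so they are more than wording. Procedures already reports follow-up counts, so any change made after outcome data were seen should be dated and labelled as such.
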